6.6.3 Specimen Preparation, Handling, Storage, and Shipping

Detailed information for collection, labeling, preparation, handling, storage, and shipping of specimens is detailed in the manual of procedures (MOP).

7 STUDY PRODUCT DESCRIPTION

7.1 Dosage and Study Drug Information

7.1.1 Rationale for Dose Selection

A dose of 30–40 mg/kg/day divided q6h or q8h with a maximum dose of 2.7 g/day is selected based on current labeling. Patients who are receiving clindamycin as part of their routine care are also eligible to participate if their dose can be adjusted to be at least 30 mg/kg/day upon enrollment. The dose administered will be based on TBW. Because bioavailability is estimated at 85%, the same dose will be used for oral administration as is used for IV dosing. Both solution and capsule preparations will be included in this study because both oral formulations are used in clinical practice, and it will allow the inclusion of those patients who cannot swallow pills. In the absence of PK data, we assume that drug clearance will be comparable in obese pediatric patients compared to non-obese pediatric patients. Therefore, a dosing regimen 30–40 mg/kg per day and a maximum dose of 2.7 g/day should provide exposures similar to those used in children and adolescents with a normal BMI. It is predicted to be safe in the obese population because similar doses are currently used per routine care.

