Protocol Title:	Safety and Pharmacokinetics of Multiple-Dose Intravenous and Oral Clindamycin in Pediatric Subjects with BMI \geq 85th Percentile (NICHHD): CLN01
Phase:	I
Product:	Clindamycin phosphate (intravenous) Clindamycin hydrochloride (oral capsules) Clindamycin palmitate (oral solution)
Objectives:	Primary: Determine the pharmacokinetics (PK) of intravenous clindamycin in overweight and obese children and adolescents Secondary: 1) Determine the PK of oral clindamycin in overweight and obese children and adolescents 2) Characterize the safety profile of clindamycin in overweight and obese children and adolescents
Study Design:	Prospective, multi-center, open-label, multiple-dose PK study of intravenous and oral clindamycin
Study Population:	Children ages 2 – <18 years of age with body mass index (BMI) \geq 85 percentile for age
Number of Participants:	24–32 evaluable participants
Number of Sites:	Up to 8 sites
Duration of Subject Participation:	Up to 18 days (1-day screening period, maximum of 14-day treatment period, and 3-day observation period)
Dose Schedule:	30–40 mg/kg/day dosed every 6 or every 8 hours with a maximum daily dose of 2.7 grams/day. Dosing greater than 2.7 g/day will be allowed for children receiving clindamycin as standard of care.
Estimated Start:	October 2012
Estimated Time to Complete Enrollment:	Approximately 24 months

PROTOCOL SYNOPSIS (continued)

Inclusion Criteria:	1) 2 years – <18 years of age at the time of first dose of study drug 2) Suspected or confirmed infection OR receiving intravenous clindamycin per routine care 3) Negative serum pregnancy test (if female and has reached menarche) within 24 hours prior to the first dose of study drug and agreement to practice appropriate contraceptive measures, including abstinence, from the time of the initial pregnancy test through the last dose of study drug 4) BMI \geq 85th percentile for age and sex, based on CDC recommendations 5) Obtained informed consent/HIPAA from the parent/legal guardian and assent (if applicable)

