7.1.2 Dose and Timing

Both q6h and q8h dosing will be allowed for both oral and IV dosing of clindamycin. For children receiving clindamycin as part of clinical care, this protocol will not prescribe a route of administration or dosing interval; the dose, route of administration, and dosing interval prescribed by the treating physician will be recorded on the CRF. However, if the prescribed dose is less than the lowest dose for this study, the dose of clindamycin will be changed to comply with the study dose. Dosing greater than 2.7 g/day will be allowed for children receiving clindamycin as part of clinical care. See **Section 5.2.1** for duration of therapy.

IV dosing: A minimum of 2 study doses of IV clindamycin will be administered. The dose administered will be based on TBW at 30–40 mg/kg/day divided q6h or q8h with a maximum dose of 2.7 grams/day. The drug will be administered over 30 (+/- 5) minutes. The venous access line will be flushed per local practice after completion of IV administration, and the time of the end of flush will be documented. It is preferred that the flush be ≤ 1 minute after the end of infusion.

Oral dosing: For those participants who are receiving clindamycin as a solution, they will receive 30–40 mg/kg/day divided q6h or q8h. For those participants receiving the capsule formulation, they will receive the dose of clindamycin defined in **Appendix III**. Only whole capsules will be used. The oral solution will be used for those participants who cannot swallow capsules. No more than 12 PO study drug doses will be administered as part of this study.

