APPENDIX III: CAPSULE DOSING TABLES

WT_Low	WT_High		mg/kg/day_low	mg/kg/day_high	Goal	Total Daily Dose
20	20	150/150/150/150	30.0	30.0	30 mg/kg/day	600
21	30	300/300/300	30.0	42.9	30 mg/kg/day	900
31	40	300/300/300/300	30.0	38.7	30 mg/kg/day	1200
41	45	450/450/450	30.0	32.9	30 mg/kg/day	1350
46	60	450/450/450/450	30.0	39.1	30 mg/kg/day	1800
61	72	750/750/750	31.3	36.9	30 mg/kg/day	2250
73	80	600/600/600/600	30.0	32.9	30 mg/kg/day	2400
	>81	900/900/900				2700
20	25	300/300/300	36.0	45.0	40 mg/kg/day	900
26	32	300/300/300/300	37.5	46.2	40 mg/kg/day	1200
33	38	450/450/450	35.5	40.9	40 mg/kg/day	1350
39	48	450/450/450/450	37.5	46.2	40 mg/kg/day	1800
49	56	750/750/750	40.2	45.9	40 mg/kg/day	2250
57	64	600/600/600/600	37.5	42.1	40 mg/kg/day	2400
	>64	900/900/900				2700

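### The floor, maximum, exemption and capsule table for clindamycin dosing do not agree for children over 90 kg or for capsules, and need to be reconciled

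*Supplement*

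**What the plan says.** All references are to the latest protocol version.

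- **Range and maximum.** Section 7.1.1: "A dose of 30–40 mg/kg/day divided q6h or q8h with a maximum dose of 2.7 g/day is selected based on current labeling". The synopsis dose schedule gives the same range and maximum, without separating formulations.
- **Floor for routine-care children.** Section 7.1.1 says that they "are also eligible to participate if their dose can be adjusted to be at least 30 mg/kg/day upon enrollment". Section 7.1.2 has the dose changed "if the prescribed dose is less than the lowest dose for this study".
- **Exemption from the maximum.** Section 7.1.2: "Dosing greater than 2.7 g/day will be allowed for children receiving clindamycin as part of clinical care". The synopsis: "Dosing greater than 2.7 g/day will be allowed for children receiving clindamycin as standard of care".
- **IV.** Section 7.1.2, in the paragraph after the exemption: "The dose administered will be based on TBW at 30–40 mg/kg/day divided q6h or q8h with a maximum dose of 2.7 grams/day".
- **Oral solution.** Section 7.1.2 gives the 30–40 mg/kg/day range and no maximum.
- **Capsules.** Section 7.1.2: "For those participants receiving the capsule formulation, they will receive the dose of clindamycin defined in" Appendix III. That table has two blocks, with goals of 30 and 40 mg/kg/day. Each ends in an open-ended row of 2700 mg/day, for weights above 81 kg and above 64 kg respectively.
- **Oral against IV.** Section 7.1.1 says that the oral dose equals the IV dose.

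**The concern.** A site with a heavy adolescent has to combine five statements: a floor, a maximum, an exemption, a formulation rule and a table. They do not give one answer. Depending on the sentence that the site relies on, the same child can be eligible or not, keep the current dose or have it raised, and change daily dose on switching from IV to capsules when the plan says that the dose stays the same.

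Heavy adolescents are not a marginal group here. Section 5 asks sites to prioritise BMI above the 97th percentile, up to age 18. AUC over the dosing interval is a primary outcome and depends directly on the dose given, so inconsistent instructions feed into a primary result as well as into conduct.

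**Working it through.** **1. The plan's own table.** For each weight band, low value = daily dose / upper weight and high value = daily dose / lower weight. All 13 bands with printed values reproduce to rounding, for example 1200/32 = 37.5 and 1200/26 = 46.15 (printed 46.2).

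**2. Where floor and maximum meet.** 2700 mg / 30 mg/kg = 90 kg. Beyond that:

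| Weight (kg) | 2700 mg/day gives (mg/kg/day) | 30 mg/kg/day needs (mg/day) |
|---|---|---|
| 90 | 30.0 | 2700 |
| 100 | 27.0 | 3000 |
| 120 | 22.5 | 3600 |
| 150 | 18.0 | 4500 |

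**3. Routine-care child over 90 kg on capsules.** The floor applies and the text permits more than 2.7 g/day, but the table stops at 2700 mg/day. If the IV dose at 120 kg was raised to 3600 mg/day to meet the floor, the capsule dose is 2700/3600 = 0.75 of it, or 25% lower. Section 7.1.1 says that the two are equal.

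**4. IV and solution wording.** The IV paragraph repeats the maximum without the exemption. The solution sentence has no maximum. Read alone, it gives a 120 kg child not on routine-care clindamycin at least 30 × 120 = 3600 mg/day as solution, against 2700 mg/day IV.

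**5. The lowest study dose above 90 kg.** Take a routine-care child of 120 kg on 2700 mg/day.
- If the lowest dose is 30 mg/kg/day limited by the maximum, it is 2700 mg/day and nothing changes.
- If it is 30 mg/kg/day as written in the eligibility condition, it is 3600 mg/day. The ratio is 3600/2700 = 1.33, and the child is eligible only if the dose can be raised.

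**6. Table against the 30–40 range.** The bounded rows of the goal-40 block are:

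| Band (kg) | mg/day | At upper weight | At lower weight | Whole-kg weights above 40 |
|---|---|---|---|---|
| 20–25 | 900 | 36.0 | 45.0 | 3 |
| 26–32 | 1200 | 37.5 | 46.2 | 4 |
| 33–38 | 1350 | 35.5 | 40.9 | 1 |
| 39–48 | 1800 | 37.5 | 46.2 | 6 |
| 49–56 | 2250 | 40.2 | 45.9 | 8 (all) |
| 57–64 | 2400 | 37.5 | 42.1 | 3 |

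So 25 of the 45 whole-kilogram weights from 20 to 64 exceed 40 mg/kg/day. The largest excess is 46.15/40 = 1.154, or 15.4%. The open row above 64 kg gives 2700/65 = 41.5 and stays above 40 until 2700/40 = 67.5 kg. In the goal-30 block, only 21 and 22 kg exceed 40 (900/21 = 42.9; 900/22 = 40.9).

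**7. Missing row.** The goal-30 block runs 73–80 kg and resumes above 81 kg, so 81 kg has no row.

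**The case against.** A reader might infer that the rules can never all be followed, or that every child over 90 kg must break the floor or the maximum. The documents do not support that. The floor is stated for routine-care children, and those same children are exempt from the maximum in both the synopsis and Section 7.1.2. On IV or solution they can meet the floor without breaking a rule, if the exemption is taken to govern the IV paragraph that follows it. For other children, a range with a maximum reads naturally as a weight-based dose limited by a ceiling. That a different ceiling applies by entry route is deliberate, so the difference alone is no contradiction.

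A reader might also infer that sites using Appendix III breach the dosing section. They do not, because Section 7.1.2 sends capsule dosing there. The table labels 30 and 40 as goals and prints the resulting ranges openly, and only whole 150 and 300 mg capsules are allowed. Rounding does explain 21 and 22 kg, where equal whole-capsule doses give either 600 mg/day (28.6 and 27.3 mg/kg/day) or 900 mg/day. It does not explain the rest: at the other 23 of the 25 weights in step 6, the goal-30 block lists a whole-capsule dose inside 30–40 (for example 1800/49 = 36.7 against 2250/49 = 45.9). This says nothing about which is appropriate. It shows only that capsule size does not account for the mismatch with the stated range.

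The missing maximum for solution is largely covered by the synopsis and by the statement that oral and IV doses are equal. The analysis is also fairly robust. Doses and times are recorded, clearance and volume are estimated from the doses actually given, and body-size covariates are explored. The 81 kg gap is editorial.

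What survives is the capsule conflict for routine-care children over 90 kg, the undefined lowest dose above 90 kg, the unqualified IV and solution wording, and the table against the study-wide range.

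**Conclusion.** The point stands as an internal inconsistency in the dosing text. The protocol's arithmetic is correct.

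Above 90 kg, the capsule table puts routine-care children below their stated floor (22.5 mg/kg/day at 120 kg), and the two readings of the lowest study dose differ by 33% at that weight. If kinetics are linear and the dosing interval is the same, AUC over the interval differs by the same 33%. That proportionality is an assumption. Clearance and volume should be little affected. Capsule rows exceed the study-wide upper limit by up to 15.4%. The documents do not say how many children will weigh more than 90 kg or take capsules, so the effect on the trial as a whole cannot be sized.

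The inconsistency should still be corrected: it concerns instructions that set the dose given to children and, above 90 kg, who may enrol.

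**What to change.** Reconcile the synopsis dose schedule, Sections 7.1.1 and 7.1.2 and Appendix III so that:

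- one stated rule governs both eligibility and dose above 90 kg, for each entry route and each formulation, with the lowest study dose defined there;
- the IV, solution and capsule instructions each say whether the maximum and the exemption apply, consistently with the statement that oral and IV doses are equal;
- the stated mg/kg/day range and the Appendix III rows agree, or the text says openly that capsule doses may fall outside the range and by how much;
- the 81 kg gap is closed.

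Which dose or limit applies is for the sponsor's clinicians. The cost is amendment wording and a corrected table, with no new data and no additional participants.

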7.1.2 Dose and Timing

Both q6h and q8h dosing will be allowed for both oral and IV dosing of clindamycin. For children receiving clindamycin as part of clinical care, this protocol will not prescribe a route of administration or dosing interval; the dose, route of administration, and dosing interval prescribed by the treating physician will be recorded on the CRF. However, if the prescribed dose is less than the lowest dose for this study, the dose of clindamycin will be changed to comply with the study dose. Dosing greater than 2.7 g/day will be allowed for children receiving clindamycin as part of clinical care. See **Section 5.2.1** for duration of therapy.

IV dosing: A minimum of 2 study doses of IV clindamycin will be administered. The dose administered will be based on TBW at 30–40 mg/kg/day divided q6h or q8h with a maximum dose of 2.7 grams/day. The drug will be administered over 30 (+/- 5) minutes. The venous access line will be flushed per local practice after completion of IV administration, and the time of the end of flush will be documented. It is preferred that the flush be ≤ 1 minute after the end of infusion.

Oral dosing: For those participants who are receiving clindamycin as a solution, they will receive 30–40 mg/kg/day divided q6h or q8h. For those participants receiving the capsule formulation, they will receive the dose of clindamycin defined in **Appendix III**. Only whole capsules will be used. The oral solution will be used for those participants who cannot swallow capsules. No more than 12 PO study drug doses will be administered as part of this study.

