5.1 Inclusion/Exclusion Criteria

The investigator or other study site personnel will document in the source documents (e.g., the hospital chart) that informed consent and assent (if applicable) were obtained. Laboratory tests or non-pharmacologic treatment procedures that were performed and considered “routine care” within 72 hours of first dose of study drug may be used for screening procedures required by the protocol and recorded in the case report form (CRF).

Inclusion Criteria

- 1) 2 years – < 18 years of age at the time of first dose of study drug
- 2) Suspected or confirmed infection OR receiving IV clindamycin per routine care
- 3) Negative serum pregnancy test (if female and has reached menarche) within 24 hours prior to first dose of study drug and agreement to practice appropriate contraceptive measures, including abstinence, from the time of the initial pregnancy test through the last dose of study drug
- 4) BMI ≥ 85th percentile for age and sex, based on CDC recommendations
- 5) Obtained informed consent/HIPAA from the parent/legal guardian and assent (if applicable)

Exclusion Criteria

- 1) The following apply only to those who are NOT already receiving clindamycin per routine care:
 - a. History of hypersensitivity or allergic reaction to clindamycin or lincomycin
 - b. History of *C. difficile* colitis with previous administration of clindamycin
 - c. AST > 120 units/L
 - d. ALT > 210 units/L
 - e. Total bilirubin > 3 mg/dL
 - f. Serum creatinine > 2 mg/dL
 - g. Receiving a neuromuscular blocker as part of their therapy (see **Appendix II.B**)
- 2) Previous participation in the study
- 3) Current exposure to medication listed in **Appendix II.A**

- 4) Participant is receiving extracorporeal life support (ECLS)
- 5) Participant is post-cardiac bypass (within 24 hours)
- 6) Participant on inotropes/pressors
- 7) Any other condition or chronic illness that, in the opinion of the principal investigator, makes participation unadvised or unsafe

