7.6 Concomitant Medications of Interest/Treatments

Concomitant medications of interest are listed in **Appendix II**. Children who are prescribed one of these medications after receipt of study drug may continue in the study.

REDACTED

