APPENDIX II: MEDICATIONS OF INTEREST

A. Exclusion for ALL participants at the time of enrollment:

- 1) CYP 3A4 potent inhibitors including:
 - a. Cyclosporine
 - b. Erythromycin, clarithromycin
 - c. Itraconazole, ketoconazole
 - d. Ritonavir, delavirdine, protease inhibitors
 - e. Nefazodone, fluoxetine, fluvoxamine
 - f. Verapamil and diltiazem
- 2) CYP 3A4 inducers
 - a. Rifampin,
 - b. Phenytoin
 - c. Ritonavir
- 3) Other: St. John's Wart

B. Exclusion at the time of enrollment (unless the participant was receiving these drugs prior to enrollment AND was receiving clindamycin as part of routine care prior to enrollment):

- 1) Neuromuscular blocking agents: Clindamycin may enhance neuromuscular blocking effect.
 - a. Atracurium
 - b. Cisatracurium
 - c. Pancuronium
 - d. Rocuronium
 - e. Succinylcholine
 - f. Vecuronium

The above drugs are only excluded at the time of enrollment; if a participant begins taking any of the drugs while on-study, he/she will not be discontinued.

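### A child on a neuromuscular blocker may enrol if already on routine-care clindamycin, and the study may then raise that clindamycin dose with no safeguard that names blockers

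*Supplement*

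**What the plan says.** All references are to the latest protocol version in the Supplement.

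- **Section 5.1, exclusion 1.** Items a to g open with "The following apply only to those who are NOT already receiving clindamycin per routine care". Item 1g is "Receiving a neuromuscular blocker as part of their therapy".
- **Appendix II.B.** The same exclusion holds "unless the participant was receiving these drugs prior to enrollment AND was receiving clindamycin as part of routine care prior to enrollment". The reason for listing blockers is given beside it: "Clindamycin may enhance neuromuscular blocking effect".
- **Section 7.1.2.** For routine-care children the protocol leaves route and interval to the treating physician, but "if the prescribed dose is less than the lowest dose for this study, the dose of clindamycin will be changed to comply". Section 7.1.1 makes such children eligible on condition that the dose can be brought to 30 mg/kg/day or more, and 6.3 describes the change as an increase.
- **General safeguards.** Exclusion 7 covers any other condition that "in the opinion of the principal investigator, makes participation unadvised or unsafe". Section 5.2.3 allows withdrawal at the request of the investigator or treating physician, among others.
- **Blockers started later.** Appendix II says that "if a participant begins taking any of the drugs while on-study, he/she will not be discontinued", and section 7.6 that "Children who are prescribed one of these medications after receipt of study drug may continue in the study".
- **Section 2.3.1.** The added risk to children on routine-care clindamycin is called minimal, with no exception for those whose dose the study raises.

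**The concern.** The waiver in 1g and Appendix II.B is sensible as long as the study leaves treatment alone. A child who already receives both drugs takes on no new interaction by giving blood samples. That reasoning stops applying when the study raises the clindamycin dose. Section 5.2 defines study drug as doses given after consent, so the added amount is study drug, given to meet a study dose floor, in a child whose blocker would have been disqualifying had the study been starting clindamycin.

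At stake is the consistency of a paediatric safety rule. The protocol did not leave blocker use to judgement for children new to clindamycin; it wrote a specific exclusion. For a routine-care child whose dose is raised, it relies on general judgement alone. The sentence on added risk in 2.3.1 describes continued care and does not address the increase. The blocker interaction is also absent from the risks listed in that section.

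**Working it through.** The protocol gives no figure on this point, so the check is a reading of the sections together, followed by dose arithmetic under stated assumptions.

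**Can the combination occur?**

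1. Child on a blocker, not on routine-care clindamycin: excluded by 1g and Appendix II.B.
2. Child on a blocker and on routine-care clindamycin: 1g does not apply, and the Appendix II.B exception is met. Neither provision looks at the dose.
3. Same child, prescribed less than 30 mg/kg/day: eligible under 7.1.1 if the dose can be adjusted, and 7.1.2 then directs the change. Neither 7.1.1, 7.1.2 nor 6.3 exempts blocker recipients or adds monitoring for them.
4. What could still stop it: the adjustability condition in 7.1.1, exclusion 7, and withdrawal under 5.2.3. None names blockers. Exclusions 4 to 6 (ECLS, recent bypass, inotropes or pressors) may remove some children on blockers, but not because of the blocker.

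So the text permits the combination.

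**How large would the increase be?** Rise = 30 ÷ prescribed mg/kg/day − 1. The documents give no distribution of prescribed doses, so both starting points below are assumptions.

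*Assumption A:* the 5-7 mg/kg IV dose in Appendix IV is what was prescribed. That row states no interval, so both are shown.

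| Interval | mg/kg/day | Ratio to 30 | Rise |
|---|---|---|---|
| every 6 h | 5 × 4 = 20 | 30/20 = 1.50 | +50% |
| every 6 h | 7 × 4 = 28 | 30/28 = 1.071 | +7% |
| every 8 h | 5 × 3 = 15 | 30/15 = 2.00 | +100% |
| every 8 h | 7 × 3 = 21 | 30/21 = 1.429 | +43% |

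*Assumption B:* a fixed 1800 mg/day, which no section gives as routine prescribing.

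| Weight | mg/kg/day | Floor ÷ 1800 | Rise |
|---|---|---|---|
| 60 kg | 30.0 | 1800/1800 = 1.00 | 0% |
| 70 kg | 25.7 | 2100/1800 = 1.167 | +17% |
| 80 kg | 22.5 | 2400/1800 = 1.333 | +33% |
| 90 kg | 20.0 | 2700/1800 = 1.50 | +50% |

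**Where does the cap bite?** 2700 mg ÷ 30 mg/kg = 90 kg. Above that weight the 2.7 g/day maximum lies below 30 mg/kg/day: at 110 kg it is 2700/110 = 24.5 mg/kg/day. If the cap is applied, the study would not raise such a child's dose beyond 2.7 g/day. A remedy that tests only for 30 mg/kg/day would therefore exclude some heavy children whose dose the study leaves alone.

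**The case against.** The case for leaving the text alone is substantial.

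- **Harm from the increase is inferred.** Appendix II.B warns about giving the two drugs together and says nothing about dose. A reader might infer that raising the dose is known to deepen the block; the documents do not support that. This stands and limits the point.
- **The target dose has a safety rationale.** Section 7.1.1 takes 30-40 mg/kg/day from labelling and predicts it to be safe because similar doses are in routine use. This tempers the concern and suggests that many routine-care children need little or no increase. It is silent on blockers.
- **Co-administration at full dose is accepted elsewhere.** A child on study clindamycin may start a blocker and stay in, and a blocker recipient already at the floor may enrol. That is true. There is still a difference: in those cases the clinical team knows or sets the clindamycin dose, whereas here the study changes it in a child already on a blocker.
- **The adjustability condition in 7.1.1 is an eligibility test aimed at this very step.** A careful investigator could use it to keep such a child out. It may well work in practice, but nothing in it points to blockers.
- **The treating physician may be involved.** A reader might infer that the study overrides the clinician managing the block. The documents do not say who orders the new dose, and a note to Table 1 has IV clindamycin continue per the treating physician. No claim of bypass is made.

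A reader might also extend the argument to the allergy, *C. difficile*, liver and kidney items waived under exclusion 1. This point makes no claim about them.

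**Conclusion.** The gap is real but narrow. Read together, 1g, Appendix II.B, 7.1.1, 7.1.2 and 6.3 allow the study to raise clindamycin in a child already on a neuromuscular blocker, with only general safeguards against it. The minimal-risk sentence in 2.3.1 does not address that increase.

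The number of children is unknown and probably very small. A child must be on both drugs at enrolment, below the floor, judged adjustable, and clear of exclusions 4 to 6, in a study of 24 to 32 evaluable participants. The possible increases, 0% to 50% under the fixed-dose assumption and 7% to 100% under the Appendix IV assumption, depend on assumed starting doses and, for the latter, assumed intervals. Whether any such increase would do harm cannot be settled from these documents. This is an inexpensive improvement to consider. It is not evidence that participants would be injured, and it has no bearing on the PK analysis.

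**What to change.** 1. In 5.1 (1g) and Appendix II.B, apply the blocker waiver only to routine-care children whose prescribed clindamycin dose the study would not raise: already at least 30 mg/kg/day or, where that exceeds the cap, already at 2.7 g/day. The cap clause keeps in a child above 90 kg who is at the study maximum. The same end is reached by stating in 7.1.2 that the dose of a child on a blocker is not raised.
2. In 2.3.1, limit the statement of minimal additional risk to children whose dose the study does not change.
3. Leave the rule for blockers started on study (Appendix II and 7.6) as it is.

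The cost is one clause in each place, with no new data or procedures. The downside is that at most a few children, on a blocker and below the floor, become ineligible.
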